Alternative Hypothesis: There is a difference in the mean change in ABC Irritability Subscale score from baseline to study endpoint adjusted for the baseline ABC Irritability Subscale score between active treatment and placebo groups, to the effect of -8.5 points or greater.

Rationale for Primary Efficacy Outcome Measure

Determination, application and support of the detection of a mean difference of -8.5 points between test and placebo groups in the change in the ABC Irritability Subscale score from Baseline to study Endpoint adjusted for the baseline ABC Irritability Subscale score being considered clinically relevant is based on the results of the clinical study for Abilify® (aripiprazole) that resulted in FDA clearance of the drug for the same exact intended indication as in this proposed pivotal trial combined with the results of a feasibility study employing the Erchonia® HLS Laser Device with the same device output parameters and treatment administration protocol as proposed for the current pivotal study.

Abilify® (apriprazole) Study: In the Abilify® study, the primary efficacy endpoint was the mean change from Baseline to Week 8 LOCF in the ABC Irritability Subscale score. There was a statistically significant difference between the treatment groups in favor of Abilify® (aripiprazole) in the adjusted mean change from Baseline to Week 8 LOCF (study Endpoint) in the ABC Irritability Subscale score of -7.9 (placebo -5.0, aripiprazole -12.9, difference -7.9, 95% CI (-11.7, -4.1), p<0.001). It was concluded that this change demonstrated clinically relevant and statistically significant improvement compared with placebo on the primary efficacy endpoint in the adjusted mean change from Baseline on the ABC Irritability Subscale at Endpoint.

FDA independent analysis concluded that the results of the clinical trials showed that treatment with aripiprazole is efficacious in improving the symptoms of irritability in children and adolescents with autism, as demonstrated by the results on the primary endpoint, ABC Irritability Subscale. It was stated that **aripiprazole showed clinically meaningful and statistically significant improvement compared with placebo** through study Endpoint evaluation on the primary efficacy measure of mean change from Baseline to Week 8 in the ABC Irritability Subscale score.

Therefore, the clinically significant effect size of the Erchonia® HLS Laser Device as applied to children and adolescents with autistic disorder in the proposed clinical study based on prior experience and research is defined as a minimum mean difference of -8.5 points on the ABC Irritability Subscale score from baseline to endpoint (week four) between active and placebo treatment groups.

SECONDARY EFFICACY OUTCOME MEASURES

The following secondary efficacy outcome measures will be evaluated in this study:

- ➤ Positive Response Rate: Difference in Positive Response Rate between treatment groups, where 'Positive Response Rate' is defined as satisfaction of both of the following 2 criteria:
 - ✓ >= 25% reduction from baseline to endpoint in the Aberrant Behavior Checklist (ABC) Irritability Subscale score based on the subject's primary caregiver's rating; AND
 - ✓ Clinical Global Impressions Improvement (CGI-I) scale rating of 1 or 2 (much improved or very much improved) at study endpoint as determined by the clinician's evaluation
- ➤ Mean change from baseline to endpoint in the other 4 ABC Subscale scores, based on ratings by the subject's primary caregiver:
 - ✓ Letharqy/Social Withdrawal
 - ✓ Stereotypic Behavior
 - √ Hyperactivity/Noncompliance
 - ✓ Inappropriate Speech
- ➤ Mean change from baseline to endpoint in the global ABC score
- ➤ Change in ratings on the CGI-S from baseline to study endpoint evaluation
- ➤ Change in ratings on the CGI-I from baseline to study endpoint evaluation
- Caregiver Satisfaction with Study Outcome ratings between treatment groups and across evaluations

STATISTICAL METHODS

Efficacy analysis will be according to the intent to treat (ITT) principle by last observation carried forward (LOCF).

Intent to Treat: Subjects will be included in the ITT analysis if they complete their baseline clinical assessments and had at least one post-randomization efficacy evaluation and corresponding baseline value.

Last observation carried forward (LOCF): Missing data will be handled by carrying forward the last observation for the relevant measure. The LOCF data set included date recorded at a given time point, or, if no observation was recorded at that time point, data carried forward from the previous time point with available data. Baseline data will not be carried forward or averaged to impute missing values for the LOCF data set.

STATISTICAL ANALYSIS

Primary Efficacy Analysis

For the continuous primary efficacy measure of ABC Irritability Subscale score, change scores will be evaluated by analysis of covariance (ANCOVA). The ANCOVA models for LOCF data sets will include the baseline measure as a covariate and treatment (active of placebo) as main effects.

Secondary Measures Analysis

- ➤ For the continuous secondary efficacy measures of the other 4 ABC Subscale scores, and the Global Score, change scores will be evaluated by analysis of covariance (ANCOVA). The ANCOVA models for LOCF data sets will include the baseline measure as a covariate and treatment (active of placebo) as main effects. A two-way significance level of 5% will be considered statistically significant.
- ➤ The categorical measures of the CGI will be analyzed within the framework of the generalized Cochran-Mantel Haenszel (CMH) procedure.
- Responder rate will be evaluated using Fisher's exact test to compare the proportion of responder rates between the test and control groups.

P-values will be 2-tailed tests of significance rounded to 3 decimal places. All analyses will be performed at the 5% significance level.

CAREGIVER SATISFACTION

Caregiver satisfaction ratings will be descriptively presented through the number and percentage of responses per response category. Fischer's Exact Test will be employed to determine the significance of the difference in categorical responses between treatment groups.

BLINDING EFFICACY EVALUATION

Blinding efficacy evaluation will be conducted through analysis of findings from the Caregiver and the Assessment Investigator Perceived Subject Group Allocation and Rationale responses, recorded at completion of the procedure administration phase (study endpoint).

Statistical evaluation of blinding efficacy will be performed as follows:

- (i) The percentage of caregivers who correctly perceived the subject's procedure group assignment and the percentage of caregivers who did not correctly perceive the subject's procedure group assignment will be calculated.
- (ii) The percentage of times the assessment investigators correctly perceived subjects' procedure group assignment and the percentage of times the assessment investigators did not correctly perceive subjects' procedure group assignment will be calculated.
- (iii) The **Fischer's Exact categorical analysis technique** for comparison of proportion of successes (accurate procedure group assignment determination) and failures (inaccurate procedure group assignment determination) between subject

- groups will be performed for each of the caregiver and assessment investigator determinations.
- (iv) **Qualitative analysis confirmation:** Evaluation of the comments provided by the caregiver and assessment investigators in the rationale section to explain the guess at group assignment will be evaluated and interpreted as follows to either support or negate the numerical findings:
 - Positive blinding efficacy will be supported through qualitative assessment of comments provided to support perceived group assignment that pertain to the determination being made based on treatment efficacy or lack thereof; e.g.: 'My child has been calmer and communicating better lately, so I think he got the real treatment' or 'I haven't noticed any change in my child's behavior at all, so I believe he got the fake treatment.'
 - Blinding will be determined to have failed if comments provided to support perceived group assignment pertain to factors such as sensation/visual clues, such as 'I saw/didn't see a light go on the laser', or other factors that pertain to blinding having been compromised such as 'I overheard the doctor saying my child was/wasn't getting the real treatment.'

SAFETY ANALYSES

Safety analyses will be completed on all subjects who were randomized to treatment group and received at least the first study treatment administration with the Erchonia® HLS Laser device.

Safety will be assessed by evaluating and comparing frequency and incidence of observed and/or reported adverse events between test and placebo treatment groups. A chi-square test with a continuity correction will be performed to compare the percentage of subjects who had adverse events and/or reactions between the test and placebo group subjects.

SAFETY AND CONFIDENTIALITY ISSUES

ADVERSE EVENTS

At any time throughout the study, any adverse event reported by a subject and/or subject's caregiver and/or observed by the study investigator will be recorded on the case report form and subsequently evaluated by the Principal Investigator for its relation to the study treatment and whether or not any corrective action need be taken. All applicable adverse events will be reported to the IRB and EC, if applicable.

Formal evaluation of the occurrence of any adverse events will take place at the end of each study treatment administration and each evaluation visit. In addition, subjects/caregivers will be instructed to contact the investigator at any other time that he or she believes a potential adverse event has occurred throughout the subject's participation in the clinical study.

The investigator will record the observation or report of any adverse event and assign the relationship to the study treatment on the appropriate case report form in the subject's file and will report the occurrence to the governing IRB, if and as appropriate, within 5 days of the reported occurrence, or within 24 hours in the occurrence of a serious adverse event including death.

The only known potential adverse event associated with the use of laser devices is that long-term exposure to laser light could cause damage to eyesight. As a precaution, during all laser treatment administrations with the Erchonia® HLS at the test site, both the subject and the administration investigator will wear safety glasses that filter out the laser light spectrum. The administration investigator will wear KenTek Corporation KenTek C22-KMT-6101 light blue safety glasses and the subject will wear KenTek Corporation KGOG-6101 light blue Medium Goggles safety goggles. Additional information on this safety eyewear is contained above on pages 6-8 under the section titled: DEVICE SAFETY: RISK AND PREVENTION OF EYE INJURY.

There are no other known potential adverse events from application of the study lasers. There have been no observed or reported adverse events or reactions to the application of the family of Erchonia® laser devices in several other studies using these laser devices. However, potential adverse events that may occur include, but are not necessarily limited to: skin irritation, skin discoloring, skin rash, skin indentations and infection. There may also be unknown or unanticipated risks to using the laser devices with this study treatment.

MONITORING OF THE CLINICAL STUDY

Prior to commencement of the study at any test site, the trained study Monitor(s) will provide formalized and documented training to the conduct of clinical studies in general, to the specifics of the current clinical study protocol, to the identification and reporting of adverse events and protocol deviations and to the correct set-up, operation and treatment application of the Erchonia® HLS to the study population for all study staff involved parties. A formalized Clinical Trial Monitoring Plan will be in place for real time, remote and on-site monitoring, as applicable, that will be strictly followed to ensure ongoing compliance and accuracy of procedures at the test site(s).

SUBJECT PRIVACY AND CONFIDENTIALITY

Records for each subject in the study will be maintained in separate files in a locked filing cabinet at the test site. The Principal Investigator will be responsible for ensuring that all records for a subject are stored in that subject's file at all times other than when information is being recorded on them.

Once a subject's participation in the study is complete and all of the required records are in the subject's file, copies of the documents may be made and supplied to the study Sponsor who will store them in a locked filing cabinet. Copies of subjects' case report forms will also be sent to Regulatory Insight, Inc. for the purpose of monitoring the data collection process and analysis of results. Regulatory Insight, Inc. will also maintain these copies in a separate clinical study file that is kept in a locked filing cabinet. The original records will be maintained at the test sites upon completion of the study in their original files and stored in a locked filing cabinet.

Subjects' identities will be kept confidential by assigning each subject a subject ID upon acceptance into the study. The subject ID will comprise the investigator's first and last name initials and a three-digit number that will be determined based upon the subject's order of entry into the study. For example, the eighth subject to be enrolled under Principal Investigator [name] will have a subject ID of MB008. Neither the study

Sponsor nor Regulatory Insight, Inc. will receive any additional identifying information about a subject and will therefore have no way of linking a subject ID to a particular subject and his or her results.

INFORMED CONSENT

- Informed consent will be an agreement between the study PI and each subject's designated caregiver, having the capacity to understand and make an informed decision. Consent will be obtained prior to each potential subject's participation in this clinical trial.
- The caregiver for each subject participating in this clinical trial will be made aware of the fact that the subject's participation involves research and the intent of the research, the expected duration of participation and a description of the procedures that will be followed.
- The caregiver for each subject will be made aware of the reasonably expected benefits the subject might receive, as well as any risks or potential discomfort that are involved.
- The caregiver for each subject will be made aware of alternative procedures that are available to the subject.
- The caregiver for each subject will be made aware that the subject's records will remain confidential, but that the FDA and the IRB has the right to inspect those records.
- The caregiver for each subject will be told that the subject's participation in the clinical trial is voluntary, without force or influence from the investigator or sponsor.
- The caregiver for each subject will be given the name and method of contacting the appropriate person(s) to answer any questions about the research and in the event of research-related injury.

The informed consent form can be found in **Appendix B.**

CASE REPORT FORMS

The case report forms that will be used to collect the data from each subject in this clinical trial can be found in **Appendix C**.

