- 2) The fake (placebo) Erchonia® HLS is designed to have the same physical appearance as the actual Erchonia® HLS, including the appearance of any visible light output, and neither the active nor the placebo lasers put out any notable degree of heat or noise. Therefore, there are no distinguishing factors between the active and placebo lasers for subjects or investigators. Additional information on the design, application and proven ineffectiveness of the placebo HLS Laser Device to be used in this study is contained above on pages 10-11 of this protocol document under the section titled: PLACEBO DEVICE INFORMATION.
- 3) There will be two independent investigators interacting with subjects: (i) administration investigator: who will be responsible for administrating the study treatments; (ii) assessment investigator: who will be responsible for recording the study outcome measures. Only the administration investigator will be aware of whether a subject is assigned to Treatment Group A or B, although he or she will not be made aware of whether A or B corresponds to the true or fake laser. Neither the assessment investigator nor the subject will be aware of the subject's A/B Group assignment. In this way, the assessment investigator will not be able to form an association between A/B Treatment Group and active/sham device over the course of the study if a treatment effect is observed.

4) During the laser procedures, both the subject and the administration investigator will wear safety glasses that filter out the laser light spectrum. The administration investigator will wear KenTek Corporation KenTek C22-KMT-6101 light blue safety glasses and the subject will wear KenTek Corporation KGOG-6101 light blue Medium safety goggles. Additional information on this safety eyewear is contained above on pages 6-8 under the section titled: DEVICE SAFETY: RISK AND PREVENTION OF EYE INJURY.

TREATMENT GROUP RANDOMIZATION

Subject allocation to treatment group (A or B) will be via a randomized block design with varying block sizes of two, four and six subjects. In each block, one-half of the subjects will be randomly assigned to Group A and the other half will be randomly assigned to Group B.

Randomization will be attained using computer generation sequence methodology, ensuring that the randomization methodology and the generated allocation sequence is concealed from the investigator and subjects.

Concealment will be insured as follows:

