CAREGIVER SATISFACTION WITH STUDY OUTCOME

The subject's caregiver is asked to rate how satisfied he or she is with any change in their child's autism symptoms and behaviors overall following completion of the laser administration procedures with the Erchonia® HLS by using the 5-point Likert scale presented below to respond to the following question:

"Overall, how satisfied or dissatisfied are you with any change in your child's autism symptoms and behaviors overall following the study procedures with the study laser device?"

- Very Satisfied
- Somewhat Satisfied
- Neither Satisfied nor Dissatisfied
- Not Very Satisfied
- Not at All Satisfied

The **Spanish Translation** of the study Caregiver Satisfaction with Study Outcome assessment tool that will be administered in this study will be performed by Language Scientific, Inc. The translated document will be supported by a notarized Certification of Translation

BLINDING EFFICACY EVALUATION TOOLS

Caregiver Perceived Group Allocation and Rationale

The caregiver records whether he or she believes that their child received the study treatment with the true or fake Erchonia® HLS and records verbatim his or her reasoning or rationale for this perceived determination.

Assessment Investigator Perceived Subject Group Allocation and Rationale

The Assessment Investigator records whether he or she believes the subject to have received the study treatment with the true or fake Erchonia® HLS™ and records verbatim his or her reasoning or rationale for this perceived determination.

The **Spanish Translation** of the study Blinding Efficacy Evaluation assessment tools that will be administered in this study will be performed by Language Scientific, Inc. The translated documents will be supported by a notarized Certification of Translation.

STUDY PROCEDURE PROTOCOL

PRE-TREATMENT ACTIVITIES

STUDY QUALIFICATION

SIGNING OF INFORMED CONSENT FORM

The PI will commence by presenting and reviewing in detail the items in the informed consent form with the individual's designated caregiver(s) and answer any questions he or she may have. To proceed, the individual's designated caregiver must willingly sign the informed consent form.

ASSIGNMENT OF SUBJECT IDENTIFICATION NUMBER

The subject will be assigned a unique subject identification number based upon his or her order of entry into the study.

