Following completion of the 4-week Treatment Administration Phase (after completion of all 8 treatment administrations), the following study measures will be recorded:

- Aberrant Behavior Checklist (ABC)
- Clinical Global Impressions (CGI)
- Caregiver Satisfaction with Study Outcome
- Caregiver Perceived Group Allocation and Rationale
- > Administration Investigator Perceived Group Allocation and Rationale

POST-TREATMENT EVALUATION PHASE

WEEK 8: All Subjects

Four weeks following completion of the 4-week Treatment Administration Phase (8 weeks after study onset), the following study measures will be recorded:

- ➤ Aberrant Behavior Checklist (ABC)
- Clinical Global Impressions (CGI)
- Medication and therapy use review
- > Adverse events evaluation
- > Caregiver Satisfaction with Study Outcome
- Caregiver Perceived Group Allocation and Rationale
- Administration Investigator Perceived Group Allocation and Rationale

STATISTICAL ANALYSIS PLAN

The aim of this study is to determine if the treatment effect of the Erchonia® HLS laser device for the active treatment group is greater than that for the placebo treatment group.

The study will be considered a success if, using the Intent-To-Treat (ITT) Last Observation Carried Forward (LOCF) analysis, the primary endpoint is statistically significant at the 0.05 level.

PRIMARY EFFICACY OUTCOME MEASURE

The primary efficacy outcome measure in this study is the mean change from baseline to study endpoint (end of the four-week treatment period) in the Aberrant Behavior Checklist (ABC) Irritability Subscale score.

Study success will be established through the detection of a minimum mean difference of -8.5 points between test and placebo groups in the change in ABC Irritability Subscale score from baseline to study endpoint (end of treatment week 4) adjusted for the baseline ABC Irritability Subscale score. The -8.5-point mean difference between treatment groups is considered clinically relevant with a SD of 8.9, a two-sided test with 80% power and a 5% level of significance.

Null Hypothesis: There is no difference in the mean change in ABC Irritability Subscale score from baseline to study endpoint adjusted for the baseline ABC Irritability Subscale score between active treatment and placebo groups, to the effect of less than -8.5 points.

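### The Week 4 and Week 8 schedule collects the treating investigator's allocation guess, but the blinding tool and the SAP call for the outcome assessor's guess

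*Combined protocol and SAP*

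**What the plan says.** Four parts of the combined protocol and SAP bear on this.

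- **Study Evaluation Timeline, Week 4 End and Week 8.** Both lists contain the caregiver's perceived allocation and "Administration Investigator Perceived Group Allocation and Rationale". Neither these lists nor the Week 2 list has an entry for the assessment investigator.
- **Study Test Battery, Blinding Efficacy Evaluation Tools.** Two tools are defined. One is the caregiver's. For the other, "The Assessment Investigator records whether he or she believes the subject to have received the study treatment with the true or fake" device. There is no tool for the administration investigator.
- **Statistical Analysis Plan, Blinding Efficacy Evaluation.** The data source is "the Caregiver and the Assessment Investigator Perceived Subject Group Allocation and Rationale responses, recorded at completion of the procedure administration phase (study endpoint"). Item (ii) is "The percentage of times the assessment investigators correctly perceived" the assignment, and the percentage of times they did not. Item (iii) is a Fisher's exact test that "groups will be performed for each of the caregiver and assessment investigator determinations". Item (iv) is a qualitative reading of the comments from the same two respondents.
- **Double Blind Design, item 3.** The two investigators have distinct roles. "Only the administration investigator will be aware of whether a subject is assigned to Treatment Group A or B", without being told which label is active. The other is the "assessment investigator: who will be responsible for recording the study outcome measures", who does not know the label.

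**The concern.** The visit schedule is the section that tells a site what to record and when. On this item it names a different person from the one in the tool definition and the analysis plan, and it does so at both visits.

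The protocol separates the two roles so that the person recording outcomes cannot learn to associate a label with an effect. Asking that person for a guess is the planned check that the separation worked. If the guess is taken from the treating investigator instead, the check cannot be made, and an endpoint guess not taken at Week 4 cannot be truly reconstructed later.

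The reach is limited. The responder definition has the "Irritability Subscale score based on the subject's primary caregiver's rating", so for the primary measure the caregiver's blinding matters most, and the caregiver's guess is scheduled correctly. The CGI rater is called only the physician or the clinician. If that rater is the assessment investigator, the secondary CGI measures and the CGI-I half of the responder definition would have no check on rater blinding. The documents do not settle who that rater is.

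**Working it through.** No figure in the plan needs correcting. The check is a comparison of sections and a count.

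**1. Who is asked, section by section**

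| Respondent | Tool defined (Study Test Battery) | Scheduled (Week 4 and Week 8) | Analysed (SAP, at study endpoint) |
|---|---|---|---|
| Caregiver | Yes | Yes | Yes |
| Assessment investigator | Yes | No | Yes |
| Administration investigator | No | Yes | No |

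Only the caregiver row agrees across the three sections. The two investigator rows are mirror images.

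**2. Analyses affected.** The SAP numbers its items (i) to (iv). Counted by respondent, they come to 3 types of analysis (percentage correct, Fisher's exact test, review of comments) × 2 respondents = 6. The schedule supplies data for the 3 caregiver analyses. It supplies none for item (ii) or for the assessor parts of (iii) and (iv): 3 of 6.

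**3. Guesses affected.** Subject Sample Size gives 20 per group enrolled and 18 per group evaluable. The Week 4 guesses expected per respondent type are therefore 2 × 18 = 36 to 2 × 20 = 40. Under the schedule as written:

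- caregiver: 36 to 40
- assessment investigator: 0
- administration investigator: up to 40 at Week 4 and up to 40 more at Week 8, with no planned analysis

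The 18 per group is the efficacy sample-size target, used here only as a lower bound on the number of children reaching Week 4.

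**4. Can the scheduled guess substitute for the missing one?** No, for two reasons.

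- It says nothing about the blinding of the person who records outcomes.
- The treating investigator knows the label, so guesses for children who share a label are not independent. Once that person decides that one label is active, the natural course is to guess the same way for every child carrying it. In the extreme, guesses are correct for 20/20 and 20/20, or for 0/20 and 0/20. Item (iii) compares the proportion correct between groups. With identical proportions, Fisher's exact test gives p = 1 in both cases, including the case where the active device has been fully identified.

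**5. Timing.** Guesses are scheduled at Week 4 and Week 8, but the SAP takes only those recorded at study endpoint, which is Week 4. The loss comes from the Week 4 entry. The Week 8 guesses, from any respondent, feed no planned analysis.

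**The case against.** The best reply is that this is a wording slip with little practical risk. The assessor guess is called for in two other sections, and the SAP fixes its timing at study endpoint. A site following the schedule literally would need an administration-investigator form that the Study Test Battery does not define. What is actually collected depends on the case report forms (Appendix C), which were not part of the reviewed text. Site training and real-time, remote and on-site monitoring could catch the error. No success criterion depends on the blinding evaluation. The 3 of 6 count splits the SAP's four items by respondent, and it adds little to saying that there would be no assessor guesses. Unblinding comes only after the database is sealed, so a still-blinded assessor could be asked late, if imperfectly.

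Much of this stands. The loss is conditional, the primary analysis is untouched, and a slip is the likeliest explanation. The Week 8 point is a matter of tidiness: collecting something that is not analysed is no contradiction, and the ABC and CGI at Week 8 are in the same position.

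What does not follow is that the text can be left alone. No section reconciles the conflict, the wrong role appears twice in the operative schedule, and the protocol and forms are to be translated into Spanish for the Mexico site, so the wording would carry over. A late guess is also not the endpoint guess that the SAP specifies.

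**Conclusion.** The inconsistency is certain on the face of the documents: the schedule asks for a guess that has no defined tool and no planned analysis, and it omits one that has both. The consequence is conditional. If the schedule is followed, there are no assessor guesses at Week 4 (0 of 36 to 40), and the assessor half of the blinding evaluation cannot be done. If the case report forms follow the tool definition and the SAP, nothing is lost. Which of these applies cannot be told from the reviewed text.

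The caregiver blinding analyses, the primary efficacy analysis and the sample size are not affected. Any effect on the CGI measures rests on the further assumption that the assessment investigator is the CGI rater. The point is moderate in weight. It should be corrected because it removes a planned check on bias and the correction is nearly free.

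**What to change.** - **Week 4:** change the investigator entry in the Study Evaluation Timeline to the assessment investigator's perceived group allocation and rationale, so that it agrees with the Study Test Battery and the SAP. Check the matching case report form and its Spanish version, and correct them if they follow the schedule.
- **Week 8:** make the same correction and add a sentence to the SAP saying whether the Week 8 guesses, caregiver and assessor, are analysed. Otherwise drop the item at that visit.
- **Optional:** if the administration investigator's guess is also wanted, define it as a separate item and report it descriptively. It should not enter item (iii), because that person knows the labels.

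The cost is two schedule lines, one form page if affected, and one SAP sentence. No visits or staff are added.
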